3.4 Subject Replacement and Completion

A total of 24 subjects (8 in each cohort) are to fully complete the trial. Depending on the cohort, study completion is defined as:

- Cohorts 1 and 2: infused with autologous FDP and completion of the 7-day post-infusion follow-up visit; and
- Cohort 3: infused with both the autologous experimental and control products per the assigned treatment sequence and completion of the 7-day post-infusion follow-up visit subsequent to the second infusion.

In cases where subjects discontinue participation prior to study completion, a replacement subject will be enrolled in the study. The replacement, assigned a new and unique SID, will be assigned to the same treatment arm as the discontinued subject. This is necessary to maintain the 1:1 ratio between study arms.

3.5 Data and Safety Monitoring

An independent DSMB will be convened to review clinical trial safety data and provide recommendations to the USAMMDA Office of Regulated Activities Product Safety Surveillance Branch (USAMMDA ORA PSSB) about proceeding with the trial at the next cohort dose or, following Cohort 3, a recommendation about proceeding with additional planned FDP protocols. The PSSB will deliver the DSMB recommendations to the Sponsor's Representative for final decision. The USAMRMC USAMMDA ORA will communicate the final decision to the PI, who will notify the IRB. USAMRMC USAMMDA ORA will communicate the final decision to the FDA, as appropriate. A further description of the DSMB roles and responsibilities, functions, and reporting requirements is included in the DSMB charter.

4. STATISTICAL ANALYSIS CONSIDERATIONS

4.1 Sample Size and Power

The sample size for this single-site study is 24 subjects. Safety will be measured using the following primary safety endpoints: AEs, TEAEs, SAEs, SUSARs, and deaths. The selection of the sample size was based on reasonably balancing the ability to address the study's primary objective and to minimize the number of subjects potentially at risk. Different safety outcome incidence rates and sample sizes were used to calculate the precision estimates calculated and presented in Table 3; the accompanying confidence intervals are based on Clopper-Pearson and were calculated using PASS software Version 13.0.3.

As shown, a safety outcome occurring at a rate of 10% incidence in 24 subjects would have a 95% confidence interval from 1.6-29.2% and a corresponding width=27.6 at a 2-sided alpha of 0.05. To account for subject attrition and for comparison purposes, a sample size of 20 and 28, respectively, are included in the table.

Table 3. 95% Confidence Intervals and Precision (δ) for Incidence

Sample Size	Incidence		
	10%	25%	50%
20	(1.2-31.7) $\delta=30.5$	(8.7-49.1) $\delta=40.4$	(27.2-72.8) $\delta=45.6$
24	(1.6-29.2) $\delta=27.6$	(9.8-46.7) $\delta=36.9$	(29.1-70.9) $\delta=41.8$
28	(2.0-27.3) $\delta=25.4$	(10.7-44.9) $\delta=34.2$	(30.6-69.4) $\delta=38.7$

Concurrent infusions will not take place across cohorts to ensure infusions at the next higher dose do not begin until all subject infusions at the previous dose are completed. Based on the study schedule, the estimated duration for which each cohort will remain active is approximately 6 months for Cohorts 1 and 2, and for Cohort 3 approximately 7 months.

4.2 Analysis Populations

Healthy male and female volunteers determined to be acceptable WB or plasmapheresis donors based on FDA regulations and responses to the AABB Full-Length Donor History Questionnaire (Appendix B of the protocol) are eligible to provide study consent. In addition, the study considers those deferred from donating due only to travel, as outlined by the AABB Full-Length Donor History Questionnaire, as eligible to consent for potential study enrollment. All subjects subsequently enrolled must meet the study inclusion and exclusion criteria, detailed in sections 7.4 and 7.5 of the protocol.

There will be five analysis populations for this study, two full analysis populations and three safety populations.

4.2.1 Full Analysis Populations

The two full analysis populations are defined as:

- All enrolled subjects including subjects who were prematurely withdrawn from the study prior to the Infusion Visit and were never infused (**F1**); and
- Enrolled and presented for treatment at the Infusion Visit (**F2**). (F2 includes infused and not infused).

4.2.2 Safety Populations

The three subject populations for assessing safety are defined as those who:

- Receive any volume of infused product; (i.e., In Cohort 3 subjects this includes those who received a partial dose at either Infusion Visit) (**S1**);
- Receive the full infusion dose and have at least one outcome measure (**S2**); and
- Receive the full infusion dose and can be fully evaluated because in: (**S3**, or the per protocol population).
 - Cohorts 1 and 2 the subjects also minimally completed the 7-day follow-up visit; and

- Cohort 3 the subjects had both complete infusion doses and minimally completed the 7-day follow-up visit after the second infusion.

The demographic tables (Table 1.1- Table 1.20) will include all five analysis populations listed in Section 4.2 unless it is found that both full populations include the same subjects, in which case only one table for the F1 and F2 population will be produced with the title indicating that it represents the F1, F2 populations, unless otherwise specified. Likewise, if all three safety populations are found to include the same subjects, only one table will be produced with the title indicating that it represents all safety populations, the S1, S2 and S3, unless otherwise specified. This pattern of table reduction will be repeated for the remaining tables unless otherwise indicated. Subject disposition tables will include all five populations. AE tables that display overall AE incidence will include all five populations. Tables that are restricted to TEAEs will include the safety populations only. Study drug exposure will be presented in the first safety population (S1). All other analyses will be performed in the third safety population only (S3).

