# 10.1. Specification of Safety Endpoints

The investigator will review subjects' medical records and administer a focused review of systems and a physical examination to all subjects to determine the presence of symptoms or signs of coagulation abnormalities.

Primary safety endpoints will include those related to vital signs, clinical laboratory parameters (chemistry, hematology, urine analysis, and coagulation), and AEs.

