# 11.1. Description of Statistical Methods and Analysis

The primary objective of this study is to assess the safety of single infusions with RePlasTM FDP product at increasing fixed doses of either 1 unit (approximately 270 mL), 2 units (approximately 540 mL), or 3 units (approximately 810 mL) in normal healthy subjects. Safety will be assessed by evaluating vital signs, laboratory tests during and after infusion, FDP-related AEs. No formal statistical hypotheses will be tested. Demographics, medical history, and safety data will be summarized for each cohort using standard descriptive statistics. For quantitative variables, summaries will include the sample size, mean, median, standard deviation, minimum, maximum and 25th and 75th percentile. For categorical variables, summaries will include the frequency (eg, number and percent) of subjects for each outcome. Additional analytic data will be prepared and summarized using only Cohort 3 data to address the study's secondary objectives.

The demographic and subject disposition tables will include all 5 populations per Section 11.7. If it is shown that both full populations include the same subjects, only one table will be produced with the title indicating that it represents both full populations. AE tables that display overall AE incidence will include all 5 populations. Tables that are restricted to TEAEs will include the safety populations only. Study drug exposure will be presented in the first safety population. All other analyses will be performed in the third safety population only.

After the completion of each cohort and at the conclusion of the study, the DSMB will review all subjects' cumulative safety data and make a recommendation to the sponsor on whether or not to proceed to the next cohort and for cohort 3 to proceed with conducting the next planned FDP trial protocol.

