Notes: Subjects are counted at most once on each row. Subjects may be included on more than one row.

^a=Denominator for each % is the treatment group N.

^b=Denominator adjusted because gender-specific event for males: N=XX (FDP-CPD), N=XX (FDP-ACD) for Cohort 1; N=XX (FDP-CPD), N=XX (FDP-ACD) for Cohort 2; N=XX (A), N=XX (B) for Cohort 3 [for applicable PTs].

^c=Denominator adjusted because gender-specific event for females: N=XX (FDP-CPD), N=XX (FDP-ACD) for Cohort 1; N=XX (FDP-CPD), N=XX (FDP-ACD) for Cohort 2; N=XX (A), N=XX (B) for Cohort 3 [for applicable PTs].

Preferred Terms within System Organ Class are sorted in descending order of frequency based on the treatment-emergent adverse event category.

Table 9.1. - Table 9.146. XX Measures (Units) Change from Baseline Over Time (Since Treatment Emergent Change)
XX Measures (Units) Change from Baseline Over Time (Since Treatment Emergent Change) – Cohort 1 (270 mL)
Safety Population – S3 (N=XX)

FDP-1
Phase I

	Pre-Infusion		Post-Infusion			Follow-Up Visit		
			Change from Baseline to 30 Minutes		Change from Baseline to 4 Hours		Change from Baseline to 24 Hours	
Treatment	FDP-CPD	FDP - ACD	FDP-CPD	FDP-ACD	FDP-CPD	FDP-ACD	FDP-CPD	FDP-ACD
N	xx	xx	xx	xx	xx	xx	xx	xx
Mean	xx.xx	xx.xx	xx.xx	xx.xx	xx.xx	xx.xx	xx.xx	xx.xx
SD	xx.xx	xx.xx	xx.xx	xx.xx	xx.xx	xx.xx	xx.xx	xx.xx
Min	xx.xx	xx.xx	xx.xx	xx.xx	xx.xx	xx.xx	xx.xx	xx.xx
Q1	xx.xx	xx.xx	xx.xx	xx.xx	xx.xx	xx.xx	xx.xx	xx.xx
Median	xx.xx	xx.xx	xx.xx	xx.xx	xx.xx	xx.xx	xx.xx	xx.xx
Q3	xx.xx	xx.xx	xx.xx	xx.xx	xx.xx	xx.xx	xx.xx	xx.xx
Max	xx.xx	xx.xx	xx.xx	xx.xx	xx.xx	xx.xx	xx.xx	xx.xx
>ULN ^a	xx (x.x)	xx (x.x)	xx (x.x)	xx (x.x)	xx (x.x)	xx (x.x)	xx (x.x)	xx (x.x)

Programming Note: This table has been restricted to the time points pre-infusion, 30 minutes and 4 hours post infusion at the request of the investigator, except for the hematology variables where pre-infusion, 30 minutes, 4 hours, and 24 hours will be shown. This table will be generated in the S3 population only. This table will be produced for the following endpoints where data is available:

- Vital Signs:
 - Blood Pressure (mmHg)
 - Table 9.1 (Diastolic Blood Pressure (mmHg))
 - Table 9.2 (Systolic Blood Pressure (mmHg))
 - Heart Rate (beats/min) (Table 9.3)

Note: ^a=Denominator for each % is the treatment group N at each individual time point

- Respiration Rate (breaths/min) (Table 9.4)
- Temperature (°F) (Table 9.5)
- Hematology:
 - Hematocrit (%) (Table 9.6)
 - Hemoglobin (g/dL) (Table 9.7)

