XX Measures (Units) Change from Baseline Over Time Since Treatment Emergent Change – Cohort 3 (810 mL) – Infusion #1
Safety Population – S3 (N=XX)**
FDP-1
Phase I

Note: ^a=Denominator for each % is the treatment group N at each individual time point

74

Program Path:

Data source: ADVS, ADLB Cross Reference: Listing 10-12, Listing 20-23, Listing 26-27

Data extract date:

Programming Note: This table will also be repeated for Cohort 3 for the second infusion:

- Vital Signs:
 - Blood Pressure (mmHg)
 - Table 9.104 (Diastolic Blood Pressure (mmHg))
 - Table 9.105 (Systolic Blood Pressure (mmHg))
 - Heart Rate (beats/min) (Table 9.106)
 - Respiration Rate (breaths/min) (Table 9.107)
 - Temperature (°F) (Table 9.108)
- Hematology:
 - Hematocrit (%) (Table 9.109)
 - Hemoglobin (g/dL) (Table 9.110)
 - Platelet Count (10⁹/L) (Table 9.111)
 - RBC Count (10¹²/L) (Table 9.112)
 - WBC Count (10⁹/L) (Table 9.113)
- Clinical Chemistry:
 - ALP (U/L) (Table 9.114)
 - ALT (U/L) (Table 9.115)
 - AST (U/L) (Table 9.116)
 - Ionized Calcium (mg/dL) (Table 9.117)
 - Total Magnesium (mg/dL) (Table 9.118)
 - Serum pH (Table 9.119)
 - Calcium (mg/dL) (Table 9.120)
 - Chloride (mmol/L) (Table 9.121)
 - Potassium (mmol/L) (Table 9.122)
 - Sodium (mmol/L) (Table 9.123)
 - Lactic Acid (mmol/L) (Table 9.124)
 - Bicarbonate (mmol/L) (Table 9.125)
 - Glucose (mg/dL) (Table 9.126)
 - Total Bilirubin (mg/dL) (Table 9.127)
 - Total Protein (g/dL) (Table 9.128)
 - BUN (mg/dL) (Table 9.129)
 - Creatinine (mg/dL) (Table 9.130)

Note: ^a=Denominator for each % is the treatment group N at each individual time point

Program Path:

Data source: ADVS, ADLB Cross Reference: Listing 10-12, Listing 20-23, Listing 26-27

75

Data extract date:

- Coagulation Factor Tests (All Cohorts):
 - PT (sec) (Table 9.131)
 - INR(Table 9.132)
 - aPTT (sec) (Table 9.133)
- Coagulation Factor Tests (Cohort 3 only):
 - Factor I (mg/dL) (Table 9.134)
 - Factor II (% Normal) (Table 9.135)
 - Factor V (% Normal) (Table 9.136)
 - Factor VII (% Normal) (Table 9.137)
 - Factor VIII (% Normal) (Table 9.138)
 - Factor IX (% Normal) (Table 9.139)
 - Factor X (% Normal) (Table 9.140)
 - Factor XI (% Normal) (Table 9.141)
 - von Willebrand Factor Activity (%) (Table 9.142)
 - Protein C (Factor XIV Activity) (% Normal) (Table 9.143)
 - Protein S (% Normal) (Table 9.144)
 - Antithrombin III (% Normal) (Table 9.145)
 - Alpha-2 Antiplasmin (% Normal) (Table 9.146)

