Table XX. Shift Table Summary of Number of Subjects with Absolute Laboratory Values for XX Measure (Unit) Pre-Infusion vs. Max Post-Infusion

Absolute Laboratory Values for XX Measure (Unit) Pre-Infusion vs. Max Post- Infusion – Cohort 2 (540 mL)

N=number of subjects with pre-infusion ‘normal’ and at least one post-infusion value; n=among the ‘N’, number of subjects with Max. post-infusion ‘high’. High will be a greater than or equal to 20% increase from pre-infusion for PT, INR and aPTT and greater than the upper limit of normal (ULN) for all other endpoints except for D-Dimer. Normal will be a less than 20% increase from pre-infusion for PT, INR, and aPTT and lower than or equal to the ULN for all other endpoints except for D-Dimer. D-Dimer will be converted to a categorical variable where normal will be < 0.5 ug/mL FEU and high will be \geq 0.5 ug/mL FEU.

80

Program Path:

Data source:AD LB Cross Reference: Listing 26-27

Data extract date:

Safety Population – S3 (N=XX)

FDP-1

Phase I

Programming Note: For Cohort 3, the treatment arms will be unmasked for final data analysis once the study has been unblinded. This table will be produced for the following endpoints for Cohort 3 for the first infusion (Table 11.9-11.15):

- Coagulation Factor Tests:
 - PT (Table 11.9)
 - INR (Table 11.10)
 - aPTT (Table 11.11)
 - D-Dimer (ug/mL FEU) (Table 11.12)
 - PF 1+2 (pmol/L) (Table 11.13)
 - TAT (ng/mL) (Table 11.14)
 - C3a des Arg (ng/mL) (Table 11.15)

Programming Note: This table will be produced for the following endpoints for Cohort 3 for the second infusion (Table 11.16-11.22):

- Coagulation Factor Tests:
 - PT (Table 11.16)
 - INR (Table 11.17)
 - aPTT (Table 11.18)
 - D-Dimer (ug/mL FEU) (Table 11.19)
 - PF 1+2 (pmol/L) (Table 11.20)
 - TAT (ng/mL) (Table 11.21)
 - C3a des Arg (ng/mL) (Table 11.22)

Programming Note: For Cohort 3, the treatment arms will be unmasked for final data analysis after the study has been unblinded.

Table XX. Shift Table Summary of Number of Subjects with Absolute Laboratory Values for XX Measure (Unit) Pre-Infusion vs. Max Post-Infusion

Absolute Laboratory Values for XX Measure (Unit) Pre-Infusion vs. Max Post- Infusion – Cohort 3 (810 mL) – Infusion #1 Safety Population – S3 (N=XX)

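### Laboratory and vital-sign summaries (Tables 9-12, Figures 3-4) are restricted to per-protocol completers, so a subject whose infusion is cut short or missed drops out of them, in Cohort 3 even from the Infusion #1 tables

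*SAP*

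**What the plan says.** SAP 4.2.2 defines three safety populations. S1 is anyone who received any volume of product. S2 is full dose with at least one outcome measure. S3, which the SAP labels per protocol, is full dose plus the 7-day visit. For Cohort 3 the S3 condition reads: "Cohort 3 the subjects had both complete infusion doses and minimally completed the 7-day follow-up visit after the second infusion".

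Tables restricted to treatment-emergent adverse events (TEAEs) use all three safety populations, and exposure uses S1. Then comes the general rule: "All other analyses will be performed in the third safety population only (S3". Protocol 11.1 has the same rule: "All other analyses will be performed in the third safety population only".

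The shells in SAP section 5 apply it. The Table 9 programming note says "This table will be generated in the S3 population only". Tables 10, 11 and 12 and Figures 3 and 4 carry an S3 header. So do the separate Cohort 3 first-infusion versions of Tables 9, 10 and 11, for example the one titled "XX Measures (Units) Change from Baseline Over Time Since Treatment Emergent Change – Cohort 3 (810 mL) – Infusion #1". No S1 or S2 repeat of these outputs is planned.

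Protocol 10.1 describes the status of these measurements: "Primary safety endpoints will include those related to vital signs, clinical laboratory parameters (chemistry, hematology, urine analysis, and coagulation), and AEs". Protocol 11.1 also says that safety is assessed from vital signs and laboratory tests.

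**The concern.** Membership of S3 is decided by what happens after the infusion starts. Three kinds of infused subject leave the summaries: one whose infusion is cut short, one who leaves before the required 7-day visit, and a Cohort 3 subject whose second infusion is withheld or incomplete. The last also loses a fully observed first period.

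The protocol lets such exits follow from the outcome being summarized. Under 6.9.1, an abnormal PT/INR or aPTT with more than a 20% change halts product administration pending review. Under 8.2.2 the investigator may withhold an infusion because of clinical status, and under 7.6 may withdraw a subject on safety grounds. An abnormal coagulation result after infusion 1 could therefore lead to infusion 2 not being given, and that would remove the same result from the Infusion #1 tables.

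These are the only planned summaries of laboratory and vital-sign data, and they carry secondary objective 2 (similarity of changes after FDP and FFP).

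**Working it through.** **1. When the data exist and when S3 status is settled.**

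- Tables 9 and 12 are limited to pre-infusion, 30 minutes and 4 hours, plus 24 hours for hematology. Table 10 stops at 4 hours.
- S3 status is settled at about day 7 in Cohorts 1 and 2. In Cohort 3 it is settled at the 7-day visit after infusion 2 (Study Day 22).
- So values already in hand are kept or dropped because of later events.

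**2. Replacement does not settle it.** Protocol 7.6.3 and SAP 3.4 replace subjects who discontinue before completion, but their definition of completion has no full-dose condition. A partial-dose subject who attends the 7-day visit leaves S3 and is not clearly replaced. Protocol 6.6.1 and SAP 3.2 do replace Cohort 3 subjects who leave before finishing both infusion visits. S3 then refills to 8, and its denominator no longer shows the loss.

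**3. Reproducing the SAP's own interval.** SAP 4.1 uses Clopper-Pearson 95% limits:

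- lower = Beta quantile 0.025 with parameters (x, n−x+1)
- upper = Beta quantile 0.975 with parameters (x+1, n−x)

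With n = 24 and x = 0.10 × 24 = 2.4 this gives 1.61-29.19%, width 27.58. It matches the stated 1.6-29.2% and 27.6, and the other cells of SAP Table 3 also reproduce to rounding.

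**4. Same method, one affected subject.** Assumption: that subject is the only one with an abnormal post-infusion value. For x = 0 the upper limit is 1 − 0.025^(1/n); for example, 1 − 0.025^(1/8) = 36.9%.

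| Situation | All infused (S1) | S3 |
|---|---|---|
| Arm of 4, not replaced | 1/4 = 25% (0.6-80.6%) | 0/3 (0-70.8%) |
| Cohort of 8, not replaced | 1/8 = 12.5% (0.3-52.7%) | 0/7 (0-41.0%) |
| Arm of 4, replaced | 1/5 = 20% (0.5-71.6%) | 0/4 (0-60.2%) |
| Cohort of 8, replaced | 1/9 = 11.1% (0.3-48.2%) | 0/8 (0-36.9%) |

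With two or three such subjects in a cohort, each replaced, S1 shows 2/10 = 20.0% (2.5-55.6%) or 3/11 = 27.3% (6.0-61.0%). S3 still shows 0/8.

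**5. Continuous summary.** Take the INR example given with stopping rule 4 (1.0 to 1.3, a change of 0.3) and assume no change in the others.

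- n = 8: mean = 0.3/8 = 0.0375; SD = √[(0.09 − 8 × 0.0375²)/7] = 0.106; maximum 0.3.
- n = 4: mean = 0.3/4 = 0.075; SD = √[(0.09 − 4 × 0.075²)/3] = 0.15; maximum 0.3.
- S3, without that subject: mean 0, SD 0, maximum 0.

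**6. How likely is any loss?** The documents give no rate q at which infused subjects fail S3. Over an assumed range, the chance that at least one of 8 is lost is 1 − (1 − q)^8: 14.9% at q = 2%, 33.7% at 5%, 57.0% at 10% and 83.2% at 20%.

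**The case against.** The strongest reply is that the safety conclusion does not rest on these tables. Protocol 6.4.1 and 11.1.1 list the primary endpoints as TEAEs, SAEs, SUSARs and deaths, and 6.1 bases the conclusion on TEAEs alone, so 10.1 is the outlier. An INR rise to 1.3 would trigger a stopping rule and a study pause, so it would not go unnoticed. An excluded subject also stays traceable: adverse events appear in S1, the listings state no S3 limit, Table 1.21 and Figures 1-2 show who left and why, and Table 14 gives volumes in S1. The magnitude is assumed, and the interval pairs overlap heavily. Finally, the secondary objectives concern a 3-unit dose compared within subject, for which partial or unpaired data are of limited use.

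Most of this stands as a limit on the point. It confines the problem to the final-report laboratory and vital-sign summaries and the Cohort 3 secondary objectives. For a Cohort 3 subject who leaves, replacement makes 1/9 versus 0/8 the relevant comparison. Early-withdrawal visit values collected under Protocol 8.4 have no column in Tables 9, 10 or 12, so what those tables lose is mainly the 30-minute and 4-hour values.

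It does not justify S3 as the only set. Listings are not summaries. Tables 9-11 are built by infusion and Table 12 by sequence and period, with no model that needs pairs. The full-dose argument supports keeping S3 as an additional set, and it gives no reason to discard a complete first period.

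**Conclusion.** The point holds and should be fixed. Protocol and SAP agree with each other, so this is a weakness of design and not a contradiction between documents. The only planned laboratory and vital-sign summaries exclude infused subjects on the basis of later events that can be linked to the outcome.

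With one affected subject who is the only abnormal one, the observed rate falls to zero from 25% in an arm or 12.5% in a cohort without replacement, or from 20% and 11.1% with replacement. In the INR illustration the maximum change falls from 0.3 to 0. These sizes rest on that assumption, since no dropout rate is stated. If S1 and S3 turn out identical, no result changes. The TEAE, SAE and discontinuation tables, the DSMB reports (Tables 1.1-8.3 and Figures 1-2) and the TEAE-based primary conclusion are not affected.

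**What to change.** In SAP 4.2.2, Protocol 11.1 and the shell headers, produce Tables 9-12 and Figures 3-4 in S1 by product received. Use all available post-infusion values, including first-period data when the second infusion was not given, and footnote partial doses. Keep S3 as the supportive set for full-dose and paired FDP versus FFP comparisons, under the existing table-reduction rule. Table 13 can stay as it is, because it shows pre-infusion DAT only.

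The text change is one sentence in the SAP, one in the protocol (with the amendment that requires) and the headers. S1 is already defined. The Table 9 footnote already allows a varying N: "Denominator for each % is the treatment group N at each individual time point". Table 11 asks only for a normal pre-infusion value "and at least one post-infusion value".

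The costs are that N may differ by time point or period and that S1 mixes partial with full doses, hence the footnote and the retained S3 set. If S1 and S3 differ, a second set of up to 146 + 36 + 34 + 38 = 254 tables and 5 + 19 = 24 figures could be needed. If they do not differ, the reduction rule avoids the duplication.
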